1.5. Randomization and Blinding

Central randomization will be implemented in this study. The codes will be maintained within the IWRS, which has the functionality to allow the investigator to break the blind for an individual subject. Within each cohort (including the subcohort of Cohort 1), eligible subjects will be randomized 1:1:1 to receive either a low or a high dose of JNJ-53718678, or placebo. Those randomized to a placebo regimen will be subsequently randomized in a 1:1 ratio to receive either low or high volume of placebo. This results in an overall randomization scheme of 2:2:1:1 (low dose JNJ-53718678, high dose JNJ-53718678, low volume placebo, high volume placebo). Randomization will be based on a computer-generated randomization schedule prepared before the study by or under the supervision of the sponsor.

In the subcohort of Cohort 1, next to randomization to treatment group, within each treatment arm (high dose, low dose, placebo), the 6 subjects will be randomized 1:1 to 1 of 2 different PK sampling groups. In Cohort 1, next to randomization to treatment group, the first 12 subjects of each age group (subcohort not included) will be randomized 1:1 to 1 of 2 different PK sampling groups. Once 12 subjects of a particular age group have been randomized to the 2 different PK sampling groups, the investigator can assign the subsequently enrolled subjects to either of the 2 PK sampling groups, but preferably alternating between 2 different PK sampling groups.

The randomization will be balanced by using randomly permuted blocks and will be stratified by time since symptom onset at randomization (≤ 3 days and >3 days) and by presence of risk factors for severe RSV disease (otherwise healthy vs presence of [a] risk factor[s] for severe RSV disease as defined above). Stratification will be applied to each cohort separately, with exception of the subcohort. Subjects with symptom onset ≤ 3 days before randomization must account for at least 45% of all enrolled subjects in Cohorts 1 and 2. To guarantee the required balance between strata for the interim analyses, enrollment in >3 days to ≤ 5 days since symptom onset stratum might be temporarily paused prior to an interim analysis and stopped prior to the final analysis.

2. GENERAL ANALYSIS DEFINITIONS

All analysis dataset preparations and statistical analyses will be performed using SAS® version 9.2 (or higher) and utilizing R version 3.6.3, where relevant.

2.1. Visit Windows and Phase Definitions

2.1.1. Analysis Phase Definitions

Analysis phases will be constructed as defined in [Table 2](#).

Table 2: Analysis Phases

Analysis Phase [number]	Start Date/Time	End Date/Time
Screening [1]	00:00 of the date of signing the informed consent form *	1 minute before the first study drug administration in the trial
Treatment [2]	Date/time of first study drug administration in the trial	23:59 of the last day of treatment + 3 days or 23:59 of the cut-off date for the IA, whichever comes first
Follow-up [3]	1 minute after the End of Treatment Phase	23:59 of the day of trial termination (date of last contact) or 23:59 of the cut-off date for the IA, whichever comes first

* For some sites, diagnostic ICF (Dx ICF) is required if RSV infection testing is not part of SOC or the SOC RSV diagnostic assay is not approved for use in the study. The earliest date between Dx ICF and main ICF will be used as a reference.

Assessments will be assigned to analysis phases based on their date/time, but seconds will be ignored overall. If the day part of the start date of the assessment is present but the time part is missing, the assessment will be treated as if it started at 00:00 on the day of the event (unless for Adverse Events see details in [Section 6.1](#)). If the day part of the end date of the assessment is present but the time part is missing, the assessment will be treated as if it happened at 23:59 on the day of the event. No formal imputation will be done, these rules will only be applied to allocate assessments to analysis phases.

2.1.2. Baseline

In general, the baseline record is defined as the last record before the first intake of the study drug, except for the following assessments:

- For RSV RNA viral load:
 - Last available assessment within the 24h prior to or at the same time of first drug intake will be considered as baseline.
 - If no assessment within the 24h prior to or at the same time of first drug intake, but there is a result available no later than 1h post first study drug intake, the

baseline assessment will be the first assessment completed within 1h post first drug intake.

- If none of the above assessments are available, but there is an assessment available before the 24h prior to first drug intake, it will be considered as baseline.
- If none of the above, baseline, and subsequently change from baseline, will be considered missing.

- For Pediatric RSV Electronic Symptom and Outcome Rating System (PRESORS) clinician reported outcomes (ClinRO), clinical evaluation and parent/caregiver PRESORS observer reported outcomes (ObsRO), the baseline assessment will be defined as:
 - Last available assessment within the 8h prior to first drug intake.
 - If no assessment is available within 8h prior to first drug intake, but there is an assessment completed within 1h post first drug intake, then baseline assessment will be the assessment completed within 1h post first drug intake.
 - If none of the above assessments are available, but there is an assessment available before the 8h prior to first drug intake, it will be considered as baseline.
 - If none of the above, baseline, and subsequently change from baseline, will be considered missing.
- For electrocardiogram (ECG), triplicate 12-lead ECGs, approximately 1 minute apart and preferably all within 5 minutes should be performed. Baseline for continuous ECG parameters will be defined as:
 - Average of the last available complete ECG triplicate assessment prior to first dose of study drug.
 - In the absence of complete triplicate ECGs, the average of the last available ECG duplicate assessment will be considered.
 - In the absence of complete or partial triplicates, the last available single ECG can be used.
 - If none of the above, baseline, and subsequently change from baseline, will be considered missing.

A set of complete or partial triplicate ECG assessments is identified per date/time by a group identifier. Sequence number, within group identifier, can also be used to uniquely identify the relevant set of ECGs to be averaged. For continuous ECG parameters, all further analyses will be performed on the averaged ECG assessments only.

Once baseline is assigned, any assessment performed prior to the defined baseline, will be assigned to Screening. Screening visits will not be used in by-visit summary tables, only in listings. Any assessment performed after first dose of study drug on Day 1 and not considered baseline per the aforementioned definitions, will be assigned to Day 1, post-first dose of study drug (post-baseline).

2.1.3. Relative Day

Study Day 1 is defined as the date of first study drug intake. All efficacy and safety assessments at all visits will be assigned a day relative to this date.

The relative day will be defined as:

$$reldy = \text{visit date} - \text{reference date} + 1$$

for visits on or after Day 1, and

$$reldy = \text{visit date} - \text{reference date}$$

for visits before Day 1.

There is no 'Day 0'.

2.1.4. Analysis Windows for Analysis Visits and Timepoints

Listed below are the visit windows and the target days for each visit defined in the protocol.

In general, the following rules will be applied in order to have only one evaluation per subject per analysis visit:

- If two assessments fall within the same visit window, the measurement closest to the target day will be used (the time of the assessment will be ignored, only the date component will be used)
- If the assessments are equidistant, the last measurement within the interval will be used.
- If there are two measurements on the same date and time, then the measurement with the highest sequence number will be used.

Exceptions to the general rule:

- RSV RNA Viral Load

For the analyses of RSV RNA viral load (scheduled once daily), if multiple nasal swabs were taken on a single day, the above rules will only be applied after having determined the maximum RSV RNA viral load per day (regardless of sample collection setting [on-site vs homebased] and time of collection). The maximum RSV RNA viral load on a day will be used in all subsequent RSV RNA viral load analyses (e.g. time to undetectable) and for analysis visit windowing. Identified RSV RNA viral load, as assigned per analysis visit based on these rules, will be used for all subsequent by-visit RSV RNA viral load analyses. Please notice that baseline RSV RNA viral load follows the rules described in Section 2.1.2.

- Electrocardiogram

In case there is more than one assessment per analysis visit window, the following rules will be used for continuous ECG parameters, to assign only one averaged ECG assessment per analysis timepoint. Within defined visit windows:

- The average of the last available complete ECG triplicate should be considered in the first instance.

- In the absence of complete triplicate ECGs, the average of the last available ECG duplicate should be considered.
- In the absence of complete or partial triplicates, the last available single ECG assessment can be used.
- If none of the above, averaged ECG assessment at the given analysis timepoint will be considered missing.

With the implementation of Amendment #4 (dated 26 May 2020), ECG assessments are to be collected around 1h post-dose on Study Day 1 and Study Day 3. On these days, a time window of 45 min to 90 min will additionally be applied after assigning the target day:

- If ECG assessment within the time window (1h post-dose [-15 min to +30min]), same general approach to be applied (i.e. complete triplicate to be considered first, else duplicate ECG assessment, otherwise single ECG assessment if no other available).
- If ECG assessment is not within the time window (1h post-dose [-15 min to +30min]), the averaged post-dose ECG assessment closest to the target time of 1h post-dose will be considered and again applying the same general approach.

Visit windows for VL and ECG/labs are defined as in [Table 3](#).

Table 3: Visit Windows

Analysis Visit [scheduled Analysis Visit No.]	TIME INTERVAL (Day) [TARGET TIMEPOINT (Day)]	
	VL	ECG/ Safety Laboratory
Baseline[^] [0]	<=1 [1]	<=1 [1]
Day 1	NA	1h post-dose* ≥45 min to ≤90 min [1]
Day 2 [2]	>1 to 2 [2]	
Day 3 [3]	3 [3]	1h post-dose* ≥45 min to ≤90 min [3]
Day 4 [4]	4 [4]	
Day 5 [5]	5 [5]	
Day 6 [6]	6 [6]	
Day 7 [7]	7 [7]	
Day 8 [8]	8 [8]	8-9 [8]
Day 9 [9]	9 [9]	
Day 10 [10]	10 [10]	
Day 11 [11]	11 [11]	

Table 3: Visit Windows

Analysis Visit [scheduled Analysis Visit No.]	TIME INTERVAL (Day) [TARGET TIMEPOINT (Day)]	
	VL	ECG/ Safety Laboratory
Day 12 [12]	12 [12]	
Day 13 [13]		
Day 14 [14]	13-15 [14]	
Day 15 [15]		
Day 16 [16]		
Day 17 [17]		
Day 18 [18]		
Day 19 [19]		
Day 20 [20]		
Day 21 [21]	18-24 [21]	18-24 [21]
Day 22 [22]		
Day 23 [23]		
Day 24 [24]		
Day 25 [25]		
Day 26 [26]		
Day 27 [27]		
Day 28 [28]		25 to $+\infty$ [28]

[^] Baseline is defined as the last measurement before first study drug intake. Please also see Section 2.1.2

* With the implementation of Amendment #4 (dated 26 May 2020), ECG assessments are to be collected around 1h post-dose on Study Day 1 and Study Day 3. On these days, a time window of 45 min to 90 min will additionally be applied after assigning the target day.

Assessments (scheduled or unscheduled) that occur outside the visit windows (i.e. visits not being performed per protocol), may be assigned a visit window for consistency (based on the relative day). However, these assessments per assigned visits (outside the protocol schedule) will not be used in by-visit summary tables and figures but will only be shown in individual listings and figures. It should be noted that such assessments will still contribute to the identification of worst and emergent toxicity grades/abnormalities, as relevant.

PRESORS ClinRO, Clinical evaluation and PRESORS ObsRO are collected as per **Table 4**. The assessments are performed either BID or QD.

Table 4: Planned Collection of PRESORS ClinRO, PRESORS ObsRO and Clinical Evaluation

Assessments	Cohort 1		Cohort 2
	During Hospitalization	After Discharge	
PRESORS ClinRO	BID from Day 1 to Day 14 and QD from Day 15 to Day 21	Once at clinic visits	Once at clinic visits
Clinical Evaluation^f/ SBP+DBP	BID from Day 1 to Day 21 + Day 28*	Once at clinic visits + Day 28*	Once at clinic visits + Day 28*
PRESORS ObsRO	BID from Day 1 to Day 14 and QD from Day 15 to Day 21		
Body Temp Caregiver	NA	BID from Day 2 to Day 14 and QD from Day 15 to Day 21	BID from Day 1 to Day 14 and QD from Day 15 to Day 21

^f Clinical evaluation includes respiratory rate, heart rate, body temperature, and SpO2.

* Only in case of on-site visit.

Visit windows for these assessments are defined as in **Table 5**.

Table 5: Visit Windows for PRESORS ClinRO, PRESORS ObsRO, Clinical Evaluation (including SBP/DBP) and Body Temperature

Analysis Time	Time Interval	Target Time
Baseline		0
12h (Day 1.5)	>0h [§] ; 17h59min	12h
24h (Day 2.0)	18h; 29h 59 min	24h
36h (Day 2.5)	30h; 41h 59min	36h
48h (Day 3.0)	42h; 53h 59min	48h
60h (Day 3.5)	54h; 65h 59min	60h
72h (Day 4.0)	66h; 77h 59min	72h
84h (Day 4.5)	78h; 89h 59min	84h
96h (Day 5.0)	90h; 101h 59min	96h
108h (Day 5.5)	102h; 113h 59min	108h
120h (Day 6.0)	114h; 125h 59min	120h
132h (Day 6.5)	126h; 137h 59min	132h
144h (Day 7.0)	138h; 149h 59min	144h
156h (Day 7.5)	150h; 161h 59min	156h
168h (Day 8.0)	162h; 173h 59min	168h
180h (Day 8.5)	174h; 185h 59min	180h
192h (Day 9.0)	186h; 197h 59min	192h
204h (Day 9.5)	198h; 209h 59min	204h
216h (Day 10.0)	210h; 221h 59min	216h
228h (Day 10.5)	222h; 233h 59 min	228h
240h (Day 11.0)	234h; 245h 59min	240h
252h (Day 11.5)	246h; 257h 59min	252h
264h (Day 12.0)	258h; 269h 59min	264h
276h (Day 12.5)	270h; 281h 59min	276h
288h (Day 13.0)	282h; 293h 59 min	288h

Table 5: Visit Windows for PRESORS ClinRO, PRESORS ObsRO, Clinical Evaluation (including SBP/DBP) and Body Temperature

Analysis Time	Time Interval	Target Time
300h (Day 13.5)	294h; 305h 59min	300h
312h (Day 14.0)	306h; 317h 59min	312h
Day 15	Day [15] (2 AM-1:59 AM)	15
Day 16	Day [16] (2 AM-1:59 AM)	16
Day 17	Day [17] (2 AM-1:59 AM)	17
Day 18	Day [18] (2 AM-1:59 AM)	18
Day 19	Day [19] (2 AM-1:59 AM)	19
Day 20	Day [20] (2 AM-1:59 AM)	20
Day 21	Day [21] (2 AM-1:59 AM)	21
Day 22	Day [22] (2 AM-1:59 AM)	22
Day 23	Day [23] (2 AM-1:59 AM)	23
Day 24	Day [24] (2 AM-1:59 AM)	24
Day 28	Day [25, $+\infty$] (2 AM-1:59 AM)	28

^{\$} Post-baseline (excluding assessments completed within 1h post-first dose of study drug on Day1 which are considered as baseline).

From Day 15 onwards, relative day (adjusted by timeframe as in the table) will be used to define analysis visits. In case there is more than one assessment per analysis visit, the one closest to the target will be used for the summary table per analysis visit. If more than one is equally close, then the last one will be considered in the analysis.

Note: in case there is an assessment on Day 14 not covered in the 312h window, it will not be used in by-visit summary tables and figures but will only be shown in individual listings and figures. Such assessments will contribute to time to event analyses, identification of abnormalities etc., as relevant.

For analyses for which we need at most one assessment per day (e.g. for summarizing combined in- and outpatient data captured by the clinician), we take the worst over 24 hours according to **Table 6**.

Table 6: Worst per Day

Analysis time	Primary Selection ("worst hourly")	Secondary Selection* ("worst daily") TIME INTERVAL (Day) [TARGET TIMEPOINT (Day)]
Baseline		
Day 2	Worst [12h; 24h]	
Day 3	Worst [36h; 48h]	3 [3]
Day 4	Worst [60h; 72h]	
Day 5	Worst [84h; 96h]	4-6 [5]
Day 6	Worst [108h; 120h]	
Day 7	Worst [132h; 144h]	
Day 8	Worst [156h; 168h]	8-9 [8]

Table 6: Worst per Day

Analysis time	Primary Selection ("worst hourly")	Secondary Selection*
		("worst daily") TIME INTERVAL (Day) [TARGET TIMEPOINT (Day)]
Day 9	Worst [180h; 192h]	
Day 10	Worst [204h; 216h]	
Day 11	Worst [228h; 240h]	
Day 12	Worst [252h; 264h]	
Day 13	Worst [276h; 288h]	
Day 14	Worst [300h; 312h]	13-15 [14]
Day 15	Worst as per relative day (2 AM-1:59 AM) Relative day	
Day 16	Worst as per relative day [16] (2 AM-1:59 AM)	
Day 17	Worst as per relative day [17] (2 AM-1:59 AM)	
Day 18	Worst as per relative day [18] (2 AM-1:59 AM)	
Day 19	Worst as per relative day [19] (2 AM-1:59 AM)	
Day 20	Worst as per relative day [20] (2 AM-1:59 AM)	
Day 21	Worst as per relative day [21] (2 AM-1:59 AM)	18-24 [21]
Day 28	25 to $+\infty$ [28]	25 to $+\infty$ [28]

* For ClinRO and Clinical Evaluation only: the secondary selection approach will be considered in the analysis if no record is assigned to Day 3, Day 5, Day 8, Day 14 and/or Day 21 according to the rules in the primary selection column in [Table 6](#) (for subjects in Cohort 1 after hospital discharge, or for Cohort 2 subjects).

- If worst per day as per primary selection available, same value will be assigned for the secondary selection of worst per day.
- Otherwise, worst per day as per secondary selection will be derived considering all possible values within the relative day window. The worst possible result will be selected regardless of being the closest one to the target day.

Day 28 will always be assigned according to the window “25 to $+\infty$ ”. The primary and secondary selection for Day 28 will be identical as the same interval is used for both.

Additionally, each BID assessment is defined as a morning or evening assessment based on the timing of the assessment as defined in [Table 7](#).

Table 7: Time Slot in a Day for BID Days

Slot of the Day	Time
Morning	02:00 am – 13:59 pm
Evening	14:00 – 01:59 am*

* from 00:00 to 01:59 to be considered as if performed within the previous day

2.2. Pooling Algorithm for Analysis Centers

As it is anticipated that subjects will be recruited over a large number of centers, and the primary endpoint is a laboratory assessment (objective endpoint) evaluated by a central

assay, no heterogeneity of treatment effects across centers is expected. No pooling algorithm for analysis centers will be applied.

2.3. Analysis Sets

2.3.1. All Randomized Analysis Sets

2.3.1.1. All Randomized Analysis (RAND) Set

All subjects randomized, regardless of being treated or not.

2.3.2. Efficacy Analysis Set(s)

The Intent-To-Treat-infected (ITT-i) set will be used to perform the evaluation of all efficacy variables including clinical course endpoints.

The primary endpoint (viral load) and key clinical course endpoints (time to resolution of key RSV symptoms, rate of RSV-related complications, change from baseline in key RSV symptoms) might also be analyzed on the Per Protocol (PP) set.

2.3.2.1. ITT-i Set

All randomized subjects who received at least one dose of study drug and who have a centrally confirmed RSV RNA viral load of $\geq 1 \log_{10}$ copies/mL above the lower limit of quantification (LLOQ) of the RSV RT-qPCR assay at baseline. Analyses on the ITT-i set will be performed as randomized.

2.3.2.2. PP Set

All subjects in the ITT-i analysis set with the exclusion of any subjects deemed to have a major impact on the assessment of efficacy. The subjects to be excluded will be identified and documented prior to database lock based on the following criteria.

- Entered but did not satisfy criteria, violation of:
 - inclusion criteria 3, 4 or 5,
AND/OR
 - exclusion criteria 5, 9, 10, 11, 12, 13 or 16

Please see Section 4.1 and 4.2 of the protocol for full description of the criteria.

- Received wrong treatment or incorrect dose
 - The actual treatment not the same as the planned treatment
 - Subjects missed more than 1 dose (including subjects who early discontinued study medication)
- Other:
 - Unplanned unblinding has taken place during the study
 - Insufficient post-baseline RSV RNA viral load samples collected (should have at least baseline and 2 post-dose samples between Day 2 and Day 5)
- Received concomitant treatment that may affect the efficacy of the trial medication. Complete list of concomitant medications to be considered for major protocol violation will be identified and documented before the database lock.

- Missing PRESORS ObsRO:
 - at baseline
 - >1 missing for 4 consecutive assessments during BID schedule
 - >1 missing for 3 consecutive assessments during QD schedule

Note that in the PP set subjects will have been treated as randomized by definition. Analyses on the PP set will only be performed if >10% subjects in the ITT-i set are excluded from the PP set.

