 - Age groups 1, 2, and 3: matching placebo (volume of placebo suspension to match the calculated volume of the JNJ-53718678 suspension for the high dose)
 - Low volume placebo:
 - Age groups 1, 2, and 3: matching placebo (volume of placebo suspension to match the calculated volume of the JNJ-53718678 suspension for the low dose)

Post-amendment #4 (dated 26 May 2020): Cohort 1 enrollment complete with all randomized and treated subjects receiving once daily dosing for a planned treatment duration of 7 days. Cohort 2 enrollment continuing with study drug to be administered twice daily (*bis in die* [BID]) for a planned treatment duration of 7 days. Total planned 14 doses are based on bodyweight and age group, but total daily dose remains identical for both cohorts regardless of dosing regimen:

- High Dose (Cohort 2: n = 50 [target]):
 - Age group 1: 2.5 mg JNJ-53718678/kg bodyweight
 - Age group 2: 3.0 mg JNJ-53718678/kg bodyweight
 - Age group 3: 4.5 mg JNJ-53718678/kg bodyweight
- Low Dose (Cohort 2: n = 50 [target]):
 - Age group 1: 0.85 mg JNJ-53718678/kg bodyweight
 - Age group 2: 1.0 mg JNJ-53718678/kg bodyweight
 - Age group 3: 1.5 mg JNJ-53718678/kg bodyweight

- Placebo (Cohort 2: n = 50 [target]): those randomized to a placebo regimen will subsequently be randomized 1:1 to receive either:
 - High volume placebo:
 - Age groups 1, 2, and 3: matching placebo (volume of placebo suspension to match the calculated volume of the JNJ-53718678 suspension for the high dose)
 - Low volume placebo:
 - Age groups 1, 2, and 3: matching placebo (volume of placebo suspension to match the calculated volume of the JNJ-53718678 suspension for the low dose)

For analysis purposes, treatment groups will be analyzed and presented regardless of dosing regimen (QD or BID).

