4.3. Treatment Compliance

Compliance with study drug administration will be summarized descriptively by cohort, by treatment group and overall. The reasons for study drug not administered, vomiting after study drug administration and swallowing of full volume of suspension will be listed only. Compliance will be derived as:

$$\text{treatment compliance (\%)} = 100 \times \text{number of doses administered} / \text{total number of doses planned per actual exposure}$$

Where total number of planned doses are as follows:

- Prior to Amendment #4 (dated 26 May 2020): study drug administered once daily:
 - For subjects who complete 7 days of planned treatment, a total number of 7 consecutive doses are to be administered as per protocol.
 - In case of premature discontinuation of study drug, total number of doses will be based on the number of days the subject was on treatment (e.g. 1 dose per

day is planned per protocol so if subject is treated for 3 days, total number of planned doses = 3 [1 day = approximately 24 hours = 1 dose planned]).

- Post-amendment #4 (dated 26 May 2020): study drug administered twice daily:
 - For subjects who complete 7 days of planned treatment, a total of 14 consecutive doses are to be administered as per protocol.
 - In case of premature discontinuation of study drug, total number of doses will be based on the number of days the subject was on treatment (e.g. 2 doses per day are planned per protocol so if subject is treated for 3 days starting the morning of Day 1, total number of planned doses = 6 taking into account the time slot of the day of first dose of study drug [1 day = approximately 24 hours = 2 doses planned]).

Derived study drug compliance (%) will be categorized as follows:

- <80 %
- ≥80 % to ≤100 %
- >100 %

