5.2.3.1. Sensitivity Analyses

Utilizing the same methodology as described for the primary efficacy endpoint, three sensitivity analyses will be performed as follows:

- MMRM + MCP-Mod: repeat analysis but using IWRS randomization stratification factors in the model as opposed to the derived factors based on the collected eCRF data.
- MMRM + MCP-Mod: repeat analysis but using the PP analysis set (if >10% ITT-i subjects excluded from PP analysis set due to major protocol deviations).
- MMRM + MCP-Mod: repeat analysis but excluding nasal swab samples where:
 - Ribonuclease P (RNase P [housekeeping gene]): result = Target Not Detected AND
 - RSV A: result = Target Not Detected AND
 - RSV B: result = Target Not Detected

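### One per-protocol set serves all endpoints: diary gaps up to Day 21 remove children from the Day 5 viral-load analysis, and the missed-dose limit is not scaled from 7 QD to 14 BID doses

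*SAP*

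**What the plan says.** SAP Section 2.3.2 makes ITT-i the set for all efficacy evaluation. It allows PP analyses of viral load and of three key clinical endpoints: time to resolution of key RSV symptoms, RSV-related complications, and change from baseline in key RSV symptoms. Section 2.3.2.2 defines one PP set for all of them, and PP analyses run only if more than 10% of ITT-i children are excluded. Three of its criteria matter here.

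- Diaries (PRESORS ObsRO): ">1 missing for 4 consecutive assessments during BID schedule" or ">1 missing for 3 consecutive assessments during QD schedule". Table 4 in Section 2.1.4 schedules the diary "BID from Day 1 to Day 14 and QD from Day 15 to Day 21".
- Swabs: a child "should have at least baseline and 2 post-dose samples between Day 2 and Day 5".
- Doses: "Subjects missed more than 1 dose (including subjects who early discontinued study medication").

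For the primary endpoint, Section 5.2.3.1 plans to "repeat analysis but using the PP analysis set". On planned doses, Section 4.3 says of the QD course that "a total number of 7 consecutive doses are to be administered as per protocol". Section 1.2 says of the BID course that began with Amendment 4: "Total planned 14 doses are based on bodyweight and age group". Section 1.2 also keeps the total daily dose the same and analyses the treatment groups without regard to regimen.

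**The concern.** A PP analysis should remove children whose departures from protocol bear on the endpoint being analysed. Two of the criteria do not fit that purpose.

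The diary criteria run to Day 21 and are not tied to an endpoint. Viral-load AUC to Day 5 is built from swabs and already has its own swab criterion. RSV-related complications, in the modified definition of Section 5.4.1, come from emergent adverse events. So two of the four endpoints use no diary data, yet diary gaps decide who enters their PP analysis.

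The missed-dose criterion is a count. Section 4.3 gives separate planned totals for QD and BID, but Section 2.3.2.2 applies one limit to both. BID exists only in Cohort 2 after Amendment 4, so the stricter limit falls on part of one cohort and can tilt the pooled PP set towards QD children.

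Of the three sensitivity analyses of the primary endpoint in Section 5.2.3.1, PP is the only one about adherence. A difference from ITT-i could reflect late diary habits or the dosing schedule rather than adherence that matters by Day 5.

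**Working it through.** The SAP gives no expected exclusion rate, diary miss rate or dose miss rate, so there is no stated figure to reproduce. The miss rates below are assumptions.

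**Dose criterion.** Inputs: 7 planned QD doses and 14 planned BID doses (Section 4.3); exclusion at 2 or more missed.

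- Tolerated share: 1/7 = 14.3% under QD, 1/14 = 7.1% under BID, a factor of 2.
- Among children who complete 7 days, QD with 1 missed is 6/7 = 85.7% and kept; BID with 2 missed is 12/14 = 85.7% and excluded. Both lie in Section 4.3's middle compliance band of 80% to 100%.
- With independent misses at rate p per dose, P(excluded) = 1 − (1−p)^n − n·p·(1−p)^(n−1). At p = 3%: QD 1 − 0.8080 − 0.1749 = 1.7%; BID 1 − 0.6528 − 0.2827 = 6.4%.

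| Miss rate per dose | QD excluded | BID excluded |
|---|---|---|
| 1% | 0.2% | 0.8% |
| 3% | 1.7% | 6.4% |
| 5% | 4.4% | 15.3% |
| 10% | 15.0% | 41.5% |

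The twofold difference in tolerated share needs no assumption. The table needs equal, independent miss rates per dose.

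**Diary criterion.** Inputs: 26 post-baseline BID slots (12h to 312h, Table 5) and 7 QD slots (Day 15 to Day 21), 33 in all. The rule is read as 2 or more missing within any 4 consecutive BID entries or any 3 consecutive QD entries. This matches the resolution definition in Table 17 (3 recordings over 4 timepoints, or 2 over 3 later, with 1 missing allowed).

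- Pairs of missed entries that trigger exclusion: BID 25 + 24 + 23 = 72, QD 6 + 5 = 11, total 83 of 33 × 32 / 2 = 528, or 15.7%. The two misses must be close together.
- With independent misses, the probability of being kept over n slots with window w is Σ_k C(n − (w−1)(k−1), k)·p^k·(1−p)^(n−k). At p = 3%: BID 0.9431, QD 0.9907, product 0.9343, so 6.6% are excluded.

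| Miss rate per entry | Excluded, rule to Day 21 | Excluded, first 8 slots only (to 96h) |
|---|---|---|
| 3% | 6.6% | 1.5% |
| 5% | 16.4% | 3.9% |
| 10% | 47.2% | 13.4% |

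The diary rule alone passes the 10% trigger at a miss rate between 3% and 5%. Misses concentrated in a few families would lower these figures; misses bunched in time would make more pairs fall within one window.

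**Does the rule select on recovery?** The simulation lets the miss rate change at resolution, with resolution at Day 4, 7 or 11:

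- 3% before and after: 6.6% excluded in each case, no preference.
- 3% before, 6% after: 19.2%, 16.4%, 11.9%.
- 10% before, 5% after: 22.9%, 29.7%, 38.2%, the reverse order.

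**The case against.** The case for leaving the set alone has substance.

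- ITT-i is the efficacy set. The type I error procedure in Section 5.2.3.2 uses ITT-i, and no decision rule in Section 5.6 invokes PP. This stands and limits the consequence.
- The diary threshold is not arbitrary: it mirrors the resolution definition in Table 17. That justifies it for time to resolution, but not for a swab endpoint or an adverse-event endpoint.
- Section 5.3.2.2 already plans four imputation analyses for missing diaries. These address time to resolution, not who enters the viral-load PP analysis.
- Both criteria apply equally across arms. That is so, but it does not make the exclusions relevant to the Day 5 AUC or even out QD and BID.

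A reader might go further and infer that any two missed diaries exclude a child. They do not: both must fall in one window, as only 83 of 528 pairs do.

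A reader might also infer that early recoverers are removed preferentially. The SAP says nothing about diary completion after recovery, and the direction depends wholly on that assumption.

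Nor would it help to stop the diary count at first resolution. At a constant 3% miss rate, counting to Day 4 (7 entries with baseline) excludes 1.2% and counting to Day 13 (25 entries) excludes 5.5%. Truncation would itself select on outcome. It would also overlook that change from baseline at Day 8 needs Day 8 diaries from children already resolved.

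**Conclusion.** The point holds in two parts. First, diary gaps at any time to Day 21 can remove a child with complete swabs from the viral-load PP analysis. On assumed independent miss rates of 3%, 5% and 10%, this rule alone excludes about 7%, 16% and 47%, and it can decide whether PP analyses run at all. Second, the missed-dose limit is exactly twice as strict under BID as under QD as a share of the course. At an assumed 3% miss rate per dose, it excludes 6.4% against 1.7%.

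Selection on recovery is possible, because the diary rule does not stop at any endpoint-relevant time, but the SAP gives no basis for saying that it happens or in which direction. It would also be too strong to call the PP results uninterpretable: they would be harder to read as evidence on adherence. The primary inference is untouched. The SAP should be changed here, but the trial's conclusions do not depend on it.

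**What to change.** Replace the single PP set with endpoint-specific flags in Section 2.3.2.2.

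- Viral load: drop the ObsRO criteria and keep the swab criterion.
- RSV-related complications: drop the ObsRO criteria.
- Change from baseline at Day 8: apply the diary criterion over a fixed window to Day 8.
- Time to resolution: the diary criterion can stay over its fixed schedule. Do not truncate it at resolution.
- Doses: state the missed-dose criterion as a share of planned doses, the same under QD and BID. The sponsor sets the level.

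The text should also say outright that the diary rule is a moving window of 4 or 3 entries, and that the 10% trigger is judged separately for each flag.

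The cost is SAP wording and more than one PP flag to program and report. No new data are needed.
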